### **7.1.1 Temporary Interruption**

Before permanently discontinuing study treatment (regardless of whether initiated by the participant, the Investigator or Sponsor), an interruption should be considered.

Participants who have temporarily interrupted study treatment should be considered to restart as soon as medically justified in the opinion of the Investigator after discussion with Sponsor and would *revert to the protocol-specified SoA (see Section 1.3) as soon as dosing of study treatment is reinitiated*.

## **7.2 PARTICIPANT DISCONTINUATION/WITHDRAWAL FROM THE STUDY**

Participants have the right to voluntarily withdraw from the study at any time for any reason.

In addition, the Investigator has the right to withdraw a participant from the study for medical conditions that the Investigator or Sponsor determines may jeopardize the participant's safety if he/she continues in the study.

If possible, information on reason for withdrawal from the study should be obtained. The primary reason for withdrawal from the study should be documented on the appropriate eCRF. Participants will not be followed for any reason after consent has been withdrawn.

When a participant voluntarily withdraws from the study, or is withdrawn by the Investigator, samples collected until the date of withdrawal will be analyzed, unless the participant specifically requests for these to be discarded or local laws require their immediate destruction. However, if samples have been tested prior to withdrawal, results from those tests will remain as part of the overall research data. A participant's withdrawal from this study does not, by itself, constitute withdrawal of specimens donated to the Research Biosample Repository (see Section [8.8.2](#)).

Participants who withdraw from the study for safety reasons will not be replaced. Participants who withdraw from the study for other reasons may be replaced.

See SoA (Section [1.3](#)) for data to be collected at the time of study discontinuation and at safety and follow-up visits, and for any further evaluations that need to be completed.

### **7.3 LOST TO FOLLOW-UP**

A participant will be considered lost to follow-up if the participant repeatedly fails to return for scheduled visits and is unable to be contacted by the study site.

The following actions must be taken if a participant fails to return to the clinic for a required study visit:

- The site must attempt to contact the participant and reschedule the missed visit as soon as possible, counsel the participant on the importance of maintaining the assigned visit schedule and ascertain whether or not the participant wishes to and/or should continue in the study.
- Before a participant is deemed lost to follow-up, the Investigator or designee must make every effort to regain contact with the participant. These contact attempts should be documented in the participant's medical record.
- Should the participant continue to be unreachable, he/she will be considered to have withdrawn from the study.

Details regarding the discontinuation of sites or of the study as a whole are outlined in [Appendix 1](#).

## **8. STUDY ASSESSMENTS AND PROCEDURES**

Study procedures and their time-points are summarized in the Schedules of Activities (SoA; Section [1.3](#)). Protocol waivers or exemptions are not allowed.

Immediate safety concerns should be discussed with the Sponsor immediately upon occurrence or awareness to determine if the participant should continue or discontinue study treatment.

Procedures conducted as part of the participant's routine clinical management (e.g., blood count) and obtained before signing of the Informed Consent Form (ICF) may

be utilized for screening or baseline purposes provided the procedure met the protocol-specified criteria and were performed within the time-frame defined in the SoA.

Samples for laboratory tests will be sent to one or several central laboratories or to the Sponsor for analysis. Instruction manuals and supply kits will be provided for all central laboratory assessments.

Based on continuous analysis of the data in this study, any *assessment*, sample type or biomarker evaluation not considered to be critical for safety may be stopped at any time if the data from the *assessments or samples* collected does not produce useful information.

## **8.1 EFFICACY ASSESSMENTS**

Flexible sigmoidoscopy (or colonoscopy at screening if required by inclusion criteria) will be performed at the time-points specified in the SoA (see Section 1.3). The endoscopy will be centrally read and scored using the MCS-ES and UCEIS scoring systems. The Endoscopy subscore of the Mayo Score will be modified so that a value of 1 does not include friability. Sedation and preparation for colonoscopy or flexible sigmoidoscopy may follow local standards.

Mucosal biopsies will be obtained during flexible sigmoidoscopy at the most affected area 10 to 20 cm from the anal verge at screening/baseline and at Day 29 (Week 4) and Day 57 (Week 8) assessments. Biopsies will be assessed by standard histology for changes in inflammatory activity as measured by the Geboes Score ([Geboes et al. 2000](#)), Robarts Histology Index ([Mosli et al. 2017](#)) and the Nancy Histology Index ([Marchal-Bressenot et al. 2017](#)).

Additional details will be provided in the Procedural Manual.

## **8.2 SAFETY ASSESSMENTS**

Planned time-points for all safety assessments are provided in the SoA (Section 1.3).

### **8.2.1 Physical Examinations**

A complete physical examination will include, at a minimum, assessments of the cardiovascular, respiratory, gastrointestinal, dermatological and neurological, musculoskeletal in addition to head, eyes, ears, nose, throat, neck and lymph nodes systems. Height and weight will also be measured and recorded. Further examination of other body systems may be performed in case of evocative symptoms at the Investigator's discretion.

The BMI will be calculated at Screening only. Height will be recorded at Screening only and body weight will be recorded at Screening, at all subsequent physical examinations and as clinically indicated.

Skinfold thickness at the intended site of injection of the abdomen, and outside the five centimeter area directly around the navel, will be measured once on Day –1, using a skinfold caliper. The result will be reported in the eCRF.

A brief physical examination will include, at a minimum, assessments of the cardiovascular, respiratory, gastrointestinal, dermatological and neurological systems, and measurement of body weight.

A complete or abbreviated physical examination will be performed at the time-points specified in the SoA (Section 1.3) by trained medical personnel at the study center. Attention should be paid to signs and symptoms suggestive of type 3 hypersensitivity reactions.

Any abnormality identified at baseline should be recorded on the General Medical History and Baseline Conditions eCRF.

As clinically indicated, limited, symptom-directed physical examinations should be performed. Changes from baseline abnormalities should be recorded in participant's notes. New or worsened clinically significant abnormalities should be recorded as AEs on the Adverse Event eCRF.

### **8.2.2 Vital Signs**

Blood pressure (BP), pulse rate, body temperature (tympanic or oral) and respiratory rate will be assessed at the time-points specified in the SoA (Section 1.3).

Blood pressure and pulse measurements will be assessed in a supine position with a completely automated device. Manual techniques will be used only if an automated device is not available. When possible, the same arm should be used for all blood pressure measurements.

Blood pressure and pulse measurements should be preceded by at least 5 minutes of rest for the participant in a quiet setting without distractions (e.g., television, cell phones).

Single measurements of vital signs (to be taken before blood collection for laboratory tests but after ECG collection when scheduled at the same time-point) will be performed in a supine position after 5 minutes rest and will include body temperature (tympanic), systolic and diastolic blood pressure, pulse rate and respiratory rate.

The timings of assessments may be amended or the number of assessments increased during study conduct on the basis of emerging data in order to allow for optimal characterization of the effect profile.

### **8.2.3        Electrocardiograms**

TriPLICATE 12-lead ECG will be obtained as outlined in the SoA (see Section 1.3) using an ECG machine. Measurements of PR, QRS complex (QRS), QT, and QTc intervals may be performed by the instrument or calculated using an external tool. Refer to Section 4.1.3 for QTc withdrawal criteria and additional QTc readings that may be necessary.

At each time-point at which triplicate ECGs are required, three individual ECG tracings should be obtained as closely as possible in succession, but no more than 5 minutes apart. The full set of triplicates should be completed in less than 10 minutes.

To minimize variability, it is important that participants be in a resting position for  $\geq 10$  minutes prior to each ECG evaluation. Body position should be consistently maintained for each ECG evaluation to prevent changes in heart rate. Environmental distractions (e.g., television, radio, conversation) should be avoided during the pre-ECG resting period and during ECG recording. ECGs should be performed prior to any scheduled vital sign measurements and blood draws. In some cases, it may be appropriate to repeat abnormal ECGs to rule out improper lead placement as contributing to the ECG abnormality.

For safety monitoring purposes, the Investigator or designee must review, sign, and date all ECG tracings. Paper or electronic copies will be kept as part of the participant's permanent study file at the site. If considered appropriate by Roche, ECGs may be analyzed retrospectively at a central laboratory.

ECG characteristics, including heart rate, QRS duration, and PR, and QT intervals, will be recorded on the eCRF. QTcF (Fridericia's correction) and RR will be calculated and recorded on the eCRF. Changes in T-wave and U-wave morphology and overall ECG interpretation will be documented on the eCRF. T-wave information will be captured as normal or abnormal, U-wave information will be captured in two categories: absent/normal or abnormal.

### **8.2.4        Clinical Safety Laboratory Assessments**

Planned time-points for all safety assessments are provided in the SoA (see Section 1.3).

Normal ranges for the study laboratory parameters must be supplied to the Sponsor before the study starts. A list of clinical laboratory tests to be performed is provided in [Appendix 4](#) and these assessments must be conducted in accordance with the separate laboratory manual and the SoA (see Section 1.3).

The Investigator must review the laboratory report, document this review, and record any clinically relevant changes occurring during the study in the AE section of the CRF. The laboratory reports must be filed with the source documents. Clinically significant abnormal laboratory findings are those which are not associated with the underlying

disease, unless judged by the Investigator to be more severe than expected for the participant's condition.

In the event of unexplained abnormal clinically significant laboratory test values, the tests should be repeated immediately and followed up until they have returned to the normal range and/or an adequate explanation of the abnormality is found.

If such values do not return to normal/baseline within a period of time judged reasonable by the Investigator, the etiology should be identified and the Sponsor notified.

If laboratory values from non-protocol specified laboratory assessments performed at the local laboratory require a change in participant management or are considered clinically significant by the Investigator (e.g., SAE or AE or dose-modification) then, the results must be recorded in the CRF.

Results of clinical laboratory testing will be recorded on the eCRF or be received as electronically produced laboratory reports submitted directly from the local or central laboratory.

Additional blood or urine samples may be taken at the discretion of the Investigator if the results of any test fall outside the reference ranges, or clinical symptoms necessitate additional testing to monitor participant safety.

Where the clinical significance of abnormal lab results is considered uncertain, screening lab tests may be repeated before randomization to confirm eligibility.

If there is an alternative explanation for a positive urine or blood test for drugs of abuse, e.g., previous occasional intake of a medication or food containing for example, codeine, benzodiazepines or opiates, the test could be repeated to confirm washout.

Based on continuous analysis of the data in this study and other studies, any sample type not considered to be critical for safety may be stopped at any time if the data from the samples collected does not produce useful information.

### **8.2.5 Safety Biomarker Assessments**

Quantitative changes in  $T_{reg}$ ,  $T_{eff}$ , NK cells, and eosinophils will be evaluated as exploratory safety biomarkers. Cytokines IL-6, IL-8, TNF- $\alpha$  or IL-1 $\beta$  may be measured as exploratory safety biomarkers ad hoc in participants experiencing symptoms associated with injection-related reactions. These assessments are described in Sections [8.6](#) and [8.8](#).

IgE, tryptase, safety cytokines, and further exploratory safety biomarkers may be tested in case of participants experiencing signs and symptoms associated with IRRs. This includes hypersensitivity reactions.

### **8.2.6 Immunogenicity Assessments**

Blood samples for ADA will be taken as described in the SoA (Section 1.3). The date and time of each sample will be recorded in the eCRF. Additional samples will be taken in participants with clinical signs of hypersensitivity reaction for ADA evaluation (see SoA Section 1.3). In each case, for each collected ADA sample, a corresponding PK sample will be collected at the same time-point for the determination of the RO7049665 concentration (See Section 8.5). Additional ADA sampling may be required after the safety and follow-up visit (Day 99) for participants who are ADA positive at the Day 99 visit. In this instance no corresponding PK sample is needed, however a sCD25 sample should be taken.

Validated ADA assays will be employed to detect ADAs against RO7049665. Samples which are positive for ADA will be further characterized and their neutralizing capability for recombinant IL-2 will be assessed using the neutralizing antibody (Nab) assay.

If required, remaining ADA samples may also be used for assay development/validation experiments. For exploratory purposes such as epitope characterization or IgG-IgM-isotyping, samples may be analyzed by assays which are not fully validated. Such samples will be kept for up to 6 months after the finalization of the bioanalytical report.

Samples from placebo-treated participants may not be analyzed in the first instance, but retained for subsequent analysis if appropriate.

Details on sampling procedures, sample storage and shipment are documented in the sample handling manual.

### **8.2.7 Local Pain and Skin Reactivity Assessments**

Local pain and injection-site reactions (ISRs; e.g., burning, bleeding, itching, bruising, redness, hive formation, or other) will be assessed at the time-points indicated in the SoA (Section 1.3, Appendix 6). Photographs of skin may be taken on an ad hoc basis but are not required per protocol.

### **8.2.8 Clinical Outcome Assessment**

Monitoring for signs and symptoms of worsening ulcerative colitis (e.g., rectal bleeding, stool frequency, abdominal pain, fever) will take place at every clinic visit. Elevation of the partial Mayo score (physician's global assessment, rectal bleeding, and stool frequency) by more than 2 points from baseline over two consecutive visits (scheduled or unscheduled) will meet disease exacerbation criteria. If disease worsening criteria meet individual stopping criteria (see Section 4.1.4) then participants will be treated as judged appropriate by their treating physician.

### **8.2.9 Medical History and Demographic Data**

Medical history includes clinically significant diseases and all medications (e.g., prescription drugs, over-the-counter drugs, herbal or homeopathic remedies, nutritional supplements) used by the participant within 14 days prior to the screening visit.

Demographic data will include age, sex, and self-reported race/ethnicity.

## **8.3 ADVERSE EVENTS AND SERIOUS ADVERSE EVENTS**

The definitions of an AE or SAE can be found in [Appendix 2](#). The non-serious AEs of special interest and disease-related events and/or disease-related outcomes not qualifying as AEs or SAEs are discussed in Sections [8.3.6](#) and [8.3.7](#).

The Investigator and any qualified designees are responsible for ensuring that all AEs (including assessment of seriousness, severity and causality; see [Appendix 2](#)) are recorded on the Adverse Event eCRF and reported to the Sponsor in accordance with instructions provided in this section and in [Appendix 2](#).

Procedures used for recording AEs are provided in [Appendix 3](#):

- Diagnosis versus signs and symptoms:
- Injection reactions
- Other AEs
- AEs occurring secondary to other events
- Persistent or recurrent AEs
- Abnormal laboratory values
- Abnormal vital sign values
- Abnormal liver function tests
- Deaths
- Preexisting medical conditions
- Lack of efficacy or worsening of the condition being studied
- Hospitalization or prolonged hospitalization
- Patient-reported outcome data

### **8.3.1 Time Period and Frequency for Collecting Adverse Event and Serious Adverse Event Information**

The method of recording, evaluating, and assessing causality of AEs and SAEs and the procedures for completing and transmitting SAE reports are provided in [Appendix 2](#).

Investigators will seek information on adverse events at each participant's contact. All AEs, whether reported by the participant or noted by study personnel, will be recorded in the participant's medical record and on the Adverse Event eCRF as follows:

**After informed consent** has been obtained **but prior to initiation of study treatment**, only SAEs caused by a protocol-mandated intervention should be reported (e.g., SAEs related to invasive procedures such as biopsies). Any other adverse event should not be reported.

**After initiation of study treatment**, all AEs, regardless of relationship to study treatment, will be reported until the Day 99 safety and follow-up visit, or, 28 days after the last dose of study treatment in case of early termination.

**Post-study adverse events and serious adverse events:** The Investigator is not required to actively monitor participants for AEs after the final follow-up visit.

However, if the Investigator learns of any SAE (including a death) or other AEs of concern that are believed to be related to prior treatment with study treatment, at any time after a participant has been discharged from the study, and the Investigator considers the event to be reasonably related to the study treatment or study participation, the Investigator must promptly notify the Sponsor. For the procedure of reporting, see [Appendix 2](#).

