## **7.1 DISCONTINUATION OF STUDY TREATMENT**

Dosing will be stopped in a given individual as described in [Section 4.1.4](#).

Participants who discontinue study treatment prematurely will be asked to return to the clinic for a study completion/early termination visit (see [Section 8.10.3](#)) and may undergo follow-up assessments (see [Section 8.10.4](#)). See the SoA ([Section 1.3](#)) for data to be collected at the time of treatment discontinuation and follow-up and for any further evaluations that need to be completed.

The primary reason for premature study treatment discontinuation should be documented on the appropriate eCRF.

Reasons for discontinuation of study treatment (or withdrawal from the study) include, but are not limited to, the following:

- Participant withdrawal of consent at any time.
- Any medical condition that the Investigator or Sponsor determines may jeopardize the participant's safety if he or she continues in the study.
- Investigator or Sponsor determination that treatment discontinuation is in the best interest of the participant.
- Pregnancy.

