### **8.10.2       Assessments during Treatment**

Under no circumstances will participants who enroll in this study and have completed treatment as specified, be permitted to be allocated a new randomization number and re-enroll in the study.

All assessments must be performed as per SoA (see Section [1.3](#)). Assessments scheduled on the day of study treatment administration should be performed prior to administration of study treatment, unless otherwise noted in the schedule of activities. COA assessments (Section [8.2.7](#)) should be performed prior to the completion of other study assessments.

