### **8.10.3 Assessments at Study Completion/Early Termination Visit**

Participants who complete the study (defined in Section 4.4) will be asked to return to the clinic 56 days after the last dose of study drug for a follow-up visit.

Participants who discontinue from the study early will be asked to return to the clinic 28 days after the last dose of study drug for a follow-up visit.

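### Following the protocol's cross-references, participants who stop dosing after one or two doses finish required follow-up before Day 57, and the AE window for any early stopper is not clearly defined.

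*Combined protocol and SAP*

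**What the plan says.** Five parts of the protocol bear on a participant who stops dosing for good.

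- **Section 7.1 (stopping treatment).** "Participants who discontinue study treatment prematurely will be asked to return to the clinic for a study completion/early termination visit", with a reference to Section 8.10.3. They "and may undergo follow-up assessments", with a reference to Section 8.10.4. The section also points to the Schedule of Activities "for data to be collected at the time of treatment discontinuation and follow-up and for any further evaluations that need to be completed".
- **Section 7.2 (leaving the study).** It points to the same Schedule "for data to be collected at the time of study discontinuation and at safety and follow-up visits". The Schedule has one early termination visit, with no fixed day.
- **Section 8.10.3 (timing of that visit).** Study completers return 56 days after the last dose. For the rest: "Participants who discontinue from the study early will be asked to return to the clinic 28 days after the last dose of study drug". A participant who stops dosing but stays in the study is not mentioned.
- **Section 8.3.1 (AE collection).** Adverse events are reported "until the Day 99 safety and follow-up visit, or, 28 days after the last dose of study treatment in case of early termination". Early termination is not defined.
- **Section 7.1.1 (temporary interruption).** Participants who restart dosing "revert to the protocol-specified SoA (see Section 1.3) as soon as dosing of study treatment is reinitiated". No matching sentence covers permanent stoppers.

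On analysis, Section 9.3.4 names early treatment discontinuation as the main expected intercurrent event. It plans a treatment-policy estimate of change to Day 57 that includes participants who stopped early, and leaves the imputation method open if data are missing. The composite strategy covers endoscopy and overall disease activity, not histology. Table 7 summarises adverse events by coded term only.

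**The concern.** A treatment-policy estimate needs outcomes from participants who stopped. If the visit rules release them before the outcome is due, the estimate no longer describes what happened to them; it describes the imputation model. Of the three strategies in Section 9.3.4, only treatment policy uses stoppers' Day 57 values: the composite counts them as failures and the on-treatment analysis leaves them out. Histology has no composite, so stoppers enter its analysis through treatment policy alone. Scores not collected at Day 57 cannot be recovered later.

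On safety, the primary objective, Table 6 keeps every treated participant in the Safety population, so stoppers count fully in the denominator whatever their follow-up. Stopping is also informative: the triggers in Section 4.1.4 include related severe events, repeat systemic reactions, neutralizing antibodies and disease exacerbation. A shorter collection window could therefore fall on participants who have already shown a signal. If stopping rises with dose, crude incidence would compare dose groups over unequal windows. Because the wording is inconsistent, sites could also apply it differently.

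**Working it through.** **Inputs.** Doses are given on Days 1, 15, 29 and 43, and final follow-up is Day 99, stated as 8 weeks after the last dose (Section 4.1.1). The 28-day and 56-day rules come from Sections 8.3.1 and 8.10.3. Endoscopic and histologic change is analysed at Day 57 (Sections 8.1 and 9.3.4).

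**The plan's own figure.** Last dose plus 56 days: 43 + 56 = 99. This matches Day 99.

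**Two readings for a permanent stopper.**

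- *28-day reading.* The stopper counts as early termination, so follow-up ends on last-dose day + 28.
- *Stay-on-schedule reading.* The stopper remains in the study and follows the Schedule to Day 99.

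| Last dose given | 28-day rule ends | Days short of Day 57 | Days from last dose to Day 99 | Difference between readings |
|---|---|---|---|---|
| Dose 1, Day 1 | 1 + 28 = Day 29 | 57 − 29 = 28 | 99 − 1 = 98 | 99 − 29 = 70 |
| Dose 2, Day 15 | 15 + 28 = Day 43 | 57 − 43 = 14 | 99 − 15 = 84 | 99 − 43 = 56 |
| Dose 3, Day 29 | 29 + 28 = Day 57 | 0 | 99 − 29 = 70 | 99 − 57 = 42 |

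**Which reading the text favours.** Section 7.1 cites Section 8.10.3, whose title names the early termination visit and whose text gives 28 days. Section 8.3.1 uses the same term and the same 28 days. That chain leads to the 28-day reading. Against it, Section 8.10.3 limits its rule to those who leave the study, and Section 8.10.2 says "All assessments must be performed as per SoA". But Section 8.10.2 is headed as covering assessments during treatment, so it is weak support for someone no longer treated.

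**Efficacy on the 28-day reading.** After one or two doses the last required visit comes 28 or 14 days before Day 57. After three doses it falls on Day 57, so timing is no obstacle.

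**Safety on the 28-day reading.** New events are collected for 28 days after the last dose in stoppers and 56 in completers.

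**Illustration only.** The documents give no discontinuation rate. Assume one or two stoppers after dose 1 or 2 among about 8 active participants in a cohort. The share of active Day 57 values to impute is then 1/8 = 12.5% or 2/8 = 25%. If a dose level pools two cohorts (16 active), it is 1/16 = 6.25% or 2/16 = 12.5%.

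**The case against.** The strongest reply on safety is that the cross-references settle the matter at 28 days. Much of that stands. A reader might infer that the AE window is wholly open between two equal readings 42 to 70 days apart. The documents do not support that: the 28-day reading is clearly the more natural one, and those differences measure the wording conflict rather than likely practice. But accepting 28 days makes the Day 57 shortfall definite after one or two doses.

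A reader might also infer that unequal windows arise only on the 28-day reading. They do not. Under stay-on-schedule, stoppers would have 98, 84 or 70 days after the last dose against 56 in completers. That reading equalises total time from Day 1, not time after the last dose. For the same reason, a person-day loss measured against a uniform 56-day window is not a measure of this problem, since neither reading gives stoppers such a window.

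The safety consequence is also limited. Recorded events are followed (Section 8.3.3.1), later related serious events or events of concern are reported if the investigator learns of them (Section 8.3.1), and ADA-positive participants are asked back (Section 8.10.4). Near-complete washout is expected within 2 weeks of the last dose (Section 2.2.2.1). What remains exposed is mainly new late-onset events, such as the delayed hypersensitivity described in Section 2.3.

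On efficacy, the reply is that the analysis is secondary and descriptive, and that imputation is foreseen. Both are true and lower the weight. An unnamed imputation method does not, however, replace data that could have been collected at a visit already scheduled.

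Finally, a reader might take Table 1 to show that the early termination visit has no endoscopy. The later columns of the extracted table are out of line, so nothing here rests on that.

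**Conclusion.** The point holds as a cheap improvement. Sections 7.1, 8.3.1 and 8.10.3 do not carry through the distinction between stopping treatment and leaving the study. On their most natural reading, required follow-up ends on Day 29 or Day 43 after one or two doses, 28 or 14 days before the time point that the treatment-policy estimand needs. No passage keeps the Day 57 assessments for those participants. Their part of the estimate would then rest on an unspecified imputation, with no composite result to set beside it for histology.

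On the same reading, new-AE collection lasts 28 days after the last dose in stoppers and 56 in completers, with crude summaries only.

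It would be too strong to say that every stopper lacks Day 57 data, because the 28-day visit after dose 3 falls on Day 57. It would also be too strong to claim a known bias in AE incidence or in the efficacy scores: no discontinuation rate is given, so the imputed shares are illustrations. No formal hypothesis is affected.

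**What to change.** 1. Reconcile Sections 7.1, 8.3.1, 8.10.3 and the Schedule of Activities so that stopping treatment and leaving the study are distinct. State which AE collection window applies to participants who stop dosing but have not withdrawn consent.
2. State that these participants are invited to the Day 57 efficacy assessments already in the schedule, with endoscopy and biopsy optional. Where Day 57 data are not obtained, label the treatment-policy estimate as imputation-dependent. Read it beside the composite result for endoscopy and the Mayo score; for histology there is none.
3. Add an AE summary over a common window after the last dose, or exposure-adjusted rates. Either can be applied to cohorts already completed.

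The cost is amendment wording, a few extra contacts or visits per stopper, and an additional AE table. There are two downsides. Sigmoidoscopy with biopsy carries the procedure risks listed in Section 2.3 for those who accept it. Follow-up at 15 mg may also differ from that in the completed 3.5 mg and 7.5 mg cohorts; a common-window summary addresses this for adverse events but not for efficacy.
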